11.4.2. Handling of Missing Data

Element	Reporting Detail
General	
 Missing data occurs when any requested data is not provided, leading to blank fields on the collection instrument: 
 These data will be indicated by the use of a “blank” in subject listing displays. Unless all data for a specific visit are missing in which case the data is excluded from the table. Answers such as “Not applicable” and “Not evaluable” are not considered to be missing data and should be displayed as such.
Outliers	
 Any subjects excluded from the summaries and/or statistical analyses will be documented along with the reason for exclusion in the clinical study report.
IFN mRNA signatures	
 No imputation methods will be used for missing value.
IHC biomarkers	
 Change from baseline will be derived for this marker (see Section 11.2.2.2). If data is missing at any particular time point, then the change from baseline will be set to missing.
Histopathology score	
 Change from baseline score will be derived (see Section 11.2.2.2) for individual components. If one or more of the components are missing then final score will be set to missing. If a score is missing at any particular time point, then the change from baseline score will be set to missing.
Histopathology component score	
 Change from baseline score will be derived for individual components for each subject. If a score is missing at any particular time point, then the change from baseline score will be set to missing.

11.4.2.1. Handling of Missing Dates

Element	Reporting Detail
General	Partial dates will be displayed as captured in subject listing displays.

Element	Reporting Detail
Adverse Events	
 The eCRF allows for the possibility of partial dates (i.e., only month and year) to be recorded for AE start and end dates; that is, the day of the month may be missing. In such a case, the following conventions will be applied for calculating the time to onset and the duration of the event: 
 Missing Start Day: First of the month will be used unless this is before the start date of study treatment; in this case the study treatment start date will be used and hence the event is considered On-treatment Missing Stop Day: Last day of the month will be used, unless this is after the stop date of study treatment; in this case the study treatment stop date will be used. Completely missing start or end dates will remain missing, with no imputation applied. Consequently, time to onset and duration of such events will be missing. Start or end dates which are completely missing (i.e. no year specified) will remain missing, with no imputation applied.

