#### **7.4.1.1. Time period and Frequency for collecting AE and SAE information**

- Any SAEs assessed as related to study participation (e.g., protocol-mandated procedures, invasive tests, or change in existing therapy) or related to a GSK product will be recorded from the time a subject consents to participate in the study up to and including any follow-up contact.

- AEs will be collected from the start of Study Treatment until the follow-up contact (see Section 7.4.1.3), at the timepoints specified in the Time and Events Table (Section 7.1).
- Medical occurrences that begin prior to the start of study treatment but after obtaining informed consent may be recorded on the Medical History/Current Medical Conditions section of the CRF.
- All SAEs will be recorded and reported to GSK within 24 hours, as indicated in Section 12.3 Appendix 3.
- Investigators are not obligated to actively seek AEs or SAEs in former study subjects. However, if the investigator learns of any SAE, including a death, at any time after a subject has been discharged from the study, and he/she considers the event reasonably related to the study treatment or study participation, the investigator must promptly notify GSK.

NOTE: The method of recording, evaluating and assessing causality of AEs and SAEs plus procedures for completing and transmitting SAE reports to GSK are provided in [Appendix 4](#).

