11.4.2.2. Handling of Partial Dates

Element	Reporting Detail
Concomitant Medications	
 Partial dates for any concomitant medications recorded in the CRF will be imputed using the following convention: 
 If the partial date is a start date, a '01' will be used for the day and 'Jan' will be used for the month If the partial date is a stop date, a '28/29/30/31' will be used for the day (dependent on the month and year) and 'Dec' will be used for the month. The recorded partial date will be displayed in listings.
Adverse Events	
 Any partial dates for adverse events will be raised to data management. If the full date cannot be ascertained, the following assumptions will be made: 
 If the partial date is a start date, a '01' will be used for the day and 'Jan' will be used for the month. However, if these results in a date prior to Week 1 Day 1 and the event could possibly have occurred during treatment from the partial information, then the Week 1 Day 1 date will be assumed to be the start date. The AE will then be considered to start on-treatment (worst case). If the partial date is a stop date, a '28/29/30/31' will be used for the day (dependent on the month and year) and 'Dec' will be used for the month. The recorded partial date will be displayed in listings.

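### SAP 11.4.2.1 and 11.4.2.2 conflict on adverse event dates with a missing day, and the stop-date cap in 11.4.2.1 ends follow-up events before they begin

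*SAP*

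**What the plan says.** **SAP 11.4.2.1 (Handling of Missing Dates), Adverse Events row.** It covers dates recorded as month and year only: "that is, the day of the month may be missing". In that case "the following conventions will be applied for calculating the time to onset and the duration of the event".

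- Start: "First of the month will be used unless this is before the start date of study treatment". If it is before, the treatment start date is used and the event is called on-treatment.
- Stop: the last day of the month, "unless this is after the stop date of study treatment; in this case the study treatment stop date will be used".
- The same row leaves completely missing dates missing.

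**SAP 11.4.2.2 (Handling of Partial Dates), Adverse Events row.** It opens with "Any partial dates for adverse events will be raised to data management". If the full date cannot be found:

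- Start: day 01 and month January. If the result falls before Week 1 Day 1, it is moved to that day only when "the event could possibly have occurred during treatment from the partial information".
- Stop: the last day of the month, and month December. Treatment stop is not mentioned.

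**Protocol 7.4.1.1.** "AEs will be collected from the start of Study Treatment until the follow-up contact". Serious AEs related to study participation or to a sponsor product are recorded from consent. Other occurrences between consent and first dose may be entered as medical history.

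**Protocol 4.2 and 7.1.3.** Group B has 28 days of treatment and 28 days of follow-up, with the follow-up visit between Day 43 and Day 56. SAP 2.1 states that nobody was randomised in Group A, so the point concerns Group B.

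**The concern.** A month-and-year AE date falls under both sections. Two programmers could each follow the SAP correctly and derive different dates from the same record.

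Capping a stop date at the end of treatment would make sense only if AE collection ended there, and it does not. The start rule in 11.4.2.1 also lacks the plausibility condition that 11.4.2.2 contains. Safety is the primary objective and Group B was planned at about 15 subjects, so a single odd record would be noticeable. Time to onset and duration are the quantities that 11.4.2.1 says it exists to calculate.

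**Working it through.** The documents give no figure to reproduce. The check applies each rule to the same record. Duration is taken as stop - start + 1, the convention that SAP 11.3.2 uses for exposure; the SAP states no separate formula for AEs.

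**Step 1: stop date, onset after the last dose.** Let the last dose be Day 28 and the AE start on a known Day s, with s from 29 to 56. The true stop is on or after Day s, so the last day of the stop month is also on or after Day s and hence after Day 28. The cap therefore always applies:

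- imputed stop = Day 28, which is before Day s
- duration = 28 - s + 1 = 29 - s
- s = 29 gives 0; s = 35 gives -6; s = 56 gives -27

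Enumeration over assumed dates agrees: 365 treatment start dates x 28 onset days x 29 true durations = 296,380 combinations. All of them stop before they start, with durations from 0 to -27, and the two sections give different stop dates in every one.

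**Step 2: stop date, onset on treatment and resolution in follow-up.** For a true stop on Day e, with e from 29 to 56, the cap again always applies and removes e - 28 days. For example, onset Day 20 and true stop Day 40 last 40 - 20 + 1 = 21 days; the capped value is 28 - 20 + 1 = 9 days.

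**Step 3: start date.** If the recorded month contains Day 1, both sections lead to Day 1. They part when the recorded month ended before Day 1. There, 11.4.2.1 still moves the start to treatment start and calls the event on-treatment, while 11.4.2.2 leaves it before treatment. Over assumed onsets 1 to 28 days before Day 1 (365 x 28 = 10,220), 4,872 (48%) have a month that ended before Day 1. Section 11.4.2.1 moves all 4,872; 11.4.2.2 moves none. These counts show how the rules behave. They do not forecast how many events would be affected.

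**Step 4: worked records.** Assume treatment from 10 March to 6 April 2018, so that Day 56 is 4 May.

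| Recorded AE date | 11.4.2.1 | 11.4.2.2, filling missing parts only | 11.4.2.2, read literally |
|---|---|---|---|
| Onset 20 April (Day 42), stop May 2018 | stop 6 April, -13 days | stop 31 May, 42 days | stop 31 December, 256 days |
| Start February 2018 | 10 March, on-treatment | 1 February, before treatment | 1 January, before treatment |
| Start May 2018 | 1 May, after treatment | 1 May, after treatment | 1 January, before treatment |

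The last column arises because 11.4.2.2 inserts January or December without requiring that the month be missing. Neither section can be kept alone as written.

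**Step 5: where the values go.** The programming notes for Tables 2.1 to 2.4 (SAP 11.8.5) say that only total AEs are summarised. The SAP defines no on-treatment or treatment-emergent AE subset for any table. Moving a date therefore does not change those counts.

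**The case against.** The strongest reply is that little depends on this.

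- Only AEs with a partial date are touched, and 11.4.2.2 sends those to data management before anything is imputed.
- Both sections show the recorded partial date in listings.
- No table or figure of AE onset time or duration is planned.

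All of this stands, and it keeps the point small.

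A second reply is that 11.4.2.1 is meant for a missing day and 11.4.2.2 for a missing month. The text does not say so, since 11.4.2.2 claims any partial AE date. Even on that reading, the cap in 11.4.2.1 still gives the negative durations of Step 1.

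Two stronger readings are tempting, but the documents do not support them.

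- A reader might infer that one relabelled event changes a reported incidence from 0/15 to 1/15. Step 5 shows that no planned display has that numerator.
- A reader might infer that pre-treatment AEs in general would be pulled on to treatment. Protocol 7.4.1.1 starts ordinary AE collection at the first dose, and earlier occurrences may go to medical history. What remains is essentially a related serious AE, recorded between consent and first dose, in a month that ended before Day 1, with the day missing.

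**Conclusion.** Wrong as written. The two sections conflict with no order of precedence, and the 11.4.2.1 cap gives an impossible duration for every AE that has a known onset after the last dose and a missing stop day. It also shortens every AE that runs from treatment into follow-up with a missing stop day. The start rule mislabels events that the recorded month places before treatment, but its reach is narrow.

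The consequence is limited to derived time to onset, duration and on-treatment status. The documents do not say how many partial AE dates to expect, so the number of affected records cannot be stated and may be zero. The day counts assume a last dose on Day 28 and duration counted inclusively. The stop-before-start result assumes a complete start date, or an imputed one that still falls after the last dose.

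**What to change.** Replace the two AE rows with a single rule:

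1. Fill only the missing parts of the date, and keep a recorded month and year.
2. Do not cap the stop at treatment stop. Cap it at the last study contact, and never place it before the AE start.
3. Move a start to Day 1 only if the recorded partial date allows an on-treatment start.
4. Retain the statement that completely missing start or end dates stay missing. It sits in the 11.4.2.1 row and would be lost if that row were simply deleted.

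In the worked example, with last contact on Day 56 (4 May), the AE with onset 20 April and stop May 2018 would end on 4 May: 15 days instead of -13. The start recorded as February 2018 would stay before treatment.

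The cost is a change of SAP wording and the matching date derivation. No new data are needed, and the total AE counts are unaffected.

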11.4.2.2. Handling of Partial Dates

Element	Reporting Detail
Concomitant Medications	
 Partial dates for any concomitant medications recorded in the CRF will be imputed using the following convention: 
 If the partial date is a start date, a '01' will be used for the day and 'Jan' will be used for the month If the partial date is a stop date, a '28/29/30/31' will be used for the day (dependent on the month and year) and 'Dec' will be used for the month. The recorded partial date will be displayed in listings.
Adverse Events	
 Any partial dates for adverse events will be raised to data management. If the full date cannot be ascertained, the following assumptions will be made: 
 If the partial date is a start date, a '01' will be used for the day and 'Jan' will be used for the month. However, if these results in a date prior to Week 1 Day 1 and the event could possibly have occurred during treatment from the partial information, then the Week 1 Day 1 date will be assumed to be the start date. The AE will then be considered to start on-treatment (worst case). If the partial date is a stop date, a '28/29/30/31' will be used for the day (dependent on the month and year) and 'Dec' will be used for the month. The recorded partial date will be displayed in listings.

11.5. Appendix 5: Values of Potential Clinical Importance

11.5.1. Laboratory Values

Haematology				
Laboratory Parameter	Units	Category	Clinical Concern Range	
			Low Flag (< x)	High Flag (>x)
Hematocrit	Ratio of 1	Male		0.54
		Female		0.54
		Δ from BL	↓0.075	
Hemoglobin	g/L	Male		180
		Female		180
		Δ from BL	↓25	
Red Blood Cell Count (RBC)	x10 ¹² / L		4.2	5.9
Lymphocytes	x10 ⁹ / L		0.8	
Neutrophil Count	x10 ⁹ / L		1.5	
Platelet Count	x10 ⁹ / L		100	550
Monocytes	x10 ⁹ / L		0.14	1.3
Eosinophils	x10 ⁹ / L			0.55
Basophils	x10 ⁹ / L			0.22
White Blood Cell Count (WBC)	x10 ⁹ / L		3	20

Clinical Chemistry				
Laboratory Parameter	Units	Category	Clinical Concern Range	
			Low Flag (< x)	High Flag (>x)
Albumin	G/L		30	
Calcium	mmol/L		2	2.75
Creatinine	umol/L	Δ from BL		↑ 44.2
Glucose	mmol/L		3	9
Magnesium	mmol/L		0.5	1.23
Phosphorus	mmol/L		0.8	1.6
Potassium	mmol/L		3	5.5
Sodium	mmol/L		130	150
Total CO ₂	mmol/L		18	32

Liver Function				
Test Analyte	Units	Category	Clinical Concern Range	
ALT/SGPT	U/L	High	≥ 2x ULN	
AST/SGOT	U/L	High	≥ 2x ULN	
AlkPhos	U/L	High	≥ 2x ULN	
T Bilirubin	μmol/L	High	≥ 1.5xULN	
T. Bilirubin + ALT	μmol/L	High	1.5xULN T. Bilirubin	

Liver Function			
Test Analyte	Units	Category	Clinical Concern Range
	U/L		+ ≥ 2x ULN ALT

11.5.2. ECG

ECG Parameter	Units	Clinical Concern Range	
		Lower	Upper
Absolute			
Absolute QTc Interval	msec		> 450
Absolute PR Interval	msec	< 110	> 220
Absolute QRS Interval	msec	< 75	> 110
Change from Baseline			
Increase from Baseline QTc	msec		>30

11.5.3. Vital Signs

Vital Sign Parameter (Absolute)	Units	Clinical Concern Range	
		Lower	Upper
Systolic Blood Pressure	mmHg	< 85	> 160
Diastolic Blood Pressure	mmHg	< 45	> 100
Heart Rate	bpm	< 40	> 110

Vital Sign Parameter (Change from Baseline)	Units	Clinical Concern Range			
		Decrease		Increase	
		Lower	Upper	Lower	Upper
Systolic Blood Pressure	mmHg		≥ 40		≥ 40
Diastolic Blood Pressure	mmHg		≥ 20		≥ 20
Heart Rate	bpm		≥ 30		≥ 30

11.6. Appendix 6: Model Checking and Diagnostics for Statistical Analyses

11.6.1. Statistical Analysis Assumptions

Endpoint(s)	
• IFN mRNA signatures
Analysis	
• Mixed model

• Model assumptions will be applied, but appropriate adjustments maybe made based on the data.• The Kenward and Roger method for approximating the denominator degrees of freedom and correcting for bias in the estimated variance-covariance of the fixed effects will be used.• Distributional assumptions underlying the model used for analysis will be examined by obtaining a normal probability plot of the residuals and a plot of the residuals versus the fitted values (i.e. checking the normality assumption and constant variance assumption of the model respectively) to gain confidence that the model assumptions are reasonable.• If there are any departures from the distributional assumptions, alternative models will be explored using appropriate transformed data.	

11.7. Appendix 7 – Abbreviations & Trade Marks

11.7.1. Abbreviations

Abbreviation	Description
AE	Adverse Event
A&R	Analysis and Reporting
BMI	Body Mass Index
CI	Confidence Interval
CLE	Cutaneous Lupus Erythematosus
CPMS	Clinical Pharmacology Modelling & Simulation
CS	Clinical Statistics
CSR	Clinical Study Report
CTR	Clinical Trial Register
DOB	Date of Birth
DP	Decimal Places
eCRF	Electronic Case Record Form
FRP	Females of Reproductive Potential
FTIH	First Time in Human
GUI	Guidance
IA	Interim Analysis
ICH	International Conference on Harmonisation
IDSL	Integrated Data Standards Library
IFN	Interferon
IMMS	International Modules Management System
IP	Investigational Product
LET	Lupus Erythematosus Tumidus
MMRM	Mixed Model Repeated Measures
mRNA	Messenger-Ribonucleic Acid
PCI	Potential Clinical Importance
PD	Pharmacodynamic
PDMP	Protocol Deviation Management Plan
PK	Pharmacokinetic
pSYK	Phosporylated- Spleen Tyrosine Kinase
PV	Photoprovocation
QC	Quality Control
QTcF	Frederica's QT Interval Corrected for Heart Rate
QTcB	Bazett's QT Interval Corrected for Heart Rate
RAP	Reporting & Analysis Plan
RAMOS	Randomization & Medication Ordering System
RCLASI	Revised Cutaneous Lupus Erythematosus Disease Area and Severity Index
SAC	Statistical Analysis Complete
SAE	Serious Adverse Event
SOP	Standard Operation Procedure

Abbreviation	Description
SYK	Spleen Tyrosine Kinase
TA	Therapeutic Area
TFL	Tables, Figures & Listings
GSK	GlaxoSmithKline

11.7.2. Trademarks

Trademarks of the GlaxoSmithKline Group of Companies
NONE

Trademarks not owned by the GlaxoSmithKline Group of Companies
SAS
WinNonlin

11.8. Appendix 8: List of Data Displays

11.8.1. Data Display Numbering

The following numbering will be applied for RAP generated displays:

Section	Tables	Figures
Study Population	1.1 to 1.14	
Safety	2.1 to 2.20	
Efficacy	3.1	3.1 to 3.2
Pharmacokinetic	4.1 to 4.3	4.1 to 4.3
Pharmacodynamic	5.1 to 5.5	5.1 to 5.12
Section	Listings	
ICH Listings	1 to 33	
Other Listings	34 to 44	

11.8.2. Mock Example Shell Referencing

Non IDSL specifications will be referenced as indicated and if required an example mock-up displays provided in [Appendix 9: Example Mock Shells for Data Displays](#).

Section	Figure	Table	Listing
Safety	SAFE_Fn	SAFE_Tn	SAFE_Ln
Pharmacodynamic	PD_Fn	PD_Tn	PD_Ln

NOTES:

- Non-Standard displays are indicated in the 'IDSL / TST ID / Example Shell' or 'Programming Notes' column as '[Non-Standard] + Reference.'

11.8.3. Deliverable [Priority]

Delivery [Priority] ^[1]	Description
SAC	Final Statistical Analysis Complete

NOTES:

- Indicates priority (i.e. order) in which displays will be generated for the reporting effort.

11.8.4. Study Population Tables

Study Population Tables					
No.	Population	IDSL / TST ID / Example Shell	Title	Programming Notes	Deliverable [Priority]
Subject Disposition					
1.1.	Safety	CP_ES1p	Summary of Subject Disposition (Group B-Natural Lesions)		SAC
1.2.	All Screened	ES6	Summary of Reasons for Screen Failure (Group A- PV lesions)		SAC
1.3.	All Screened	ES6	Summary of Reasons for Screen Failure (Group B-Natural Lesions)		SAC
1.4.	Safety	NS1	Summary of Number of Subjects by Country and Centre (Group B-Natural Lesions)		SAC
Protocol Deviation					
1.5.	Safety	DV1	Summary of Important Protocol Deviations (Group B-Natural Lesions)		SAC
Population Analysed					
1.6.	All Screened	SP1	Summary of Study Populations and Exclusions (Group A- PV lesions)		SAC
1.7.	All Screened	SP1	Summary of Study Populations and Exclusions (Group B-Natural Lesions)		SAC

Study Population Tables					
No.	Population	IDSL / TST ID / Example Shell	Title	Programming Notes	Deliverable [Priority]
Demographic and Baseline Characteristics					
1.8.	Safety	DM3	Summary of Demographic Characteristics (Group B-Natural Lesions)	Include BMI	SAC
1.9.	Safety	DM5	Summary of Race and Racial Combinations (Group B-Natural Lesions)		SAC
1.10.	Safety	DM6	Summary of Race and Racial Combination Details (Group B-Natural Lesions)		SAC
Prior and Concomitant medications					
1.11.	Safety	MH1, MH4	Summary of [Current/Past] Medical Conditions (Group B-Natural Lesions)		SAC
1.12.	Safety	CM1	Summary of Concomitant Medications (Group B-Natural Lesions)		SAC
1.13.	Safety	SAFE_T3	Summary of Type of CLE (Group B-Natural Lesions)	Obtained from medical conditions page in eCRF. Under Disease Diagnosis – 2. Disease characteristics.	SAC
Exposure and Treatment Compliance					
1.14.	Safety	EX1	Summary of Weight of Study Cream Applied (Group B-Natural Lesions)	See Section 11.3.2 regarding total daily dose of cream; label first row as "Daily Weight of Cream (g)" with following footnote: "Note: Daily Dose refers to the one lesion that either active or placebo treatment is applied to; Label second row as "Cumulative Weight of Cream (g)".	SAC

11.8.5. Safety Tables

Safety : Tables					
No.	Population	IDSL / TST ID / Example Shell	Title	Programming Notes	Deliverable [Priority]
Adverse Events					
2.1.	Safety	CP_AE1p	Summary of All Adverse Events by System Organ Class (Group B-Natural Lesions)	Only Total adverse events will be summarised.	SAC
2.2.	Safety	CP_AE1p	Summary All Drug-Related Adverse Events by System Organ Class (Group B-Natural Lesions)	Only Total adverse events will be summarised.	SAC

Safety : Tables					
No.	Population	IDSL / TST ID / Example Shell	Title	Programming Notes	Deliverable [Priority]
Serious and Other Significant Adverse Events					
2.3.	Safety	CP_AE1p	Summary of Serious Adverse Events by System Organ Class (Group B-Natural Lesions)	Only Total adverse events will be summarised.	SAC
2.4.	Safety	CP_AE1p	Summary of Adverse Events Leading to Withdrawal from Study / Permanent Discontinuation of Study Treatment by Overall Frequency (Group B-Natural Lesions)	Only Total adverse events will be summarised.	SAC
Laboratory: Chemistry					
2.5.	Safety	LB1	Summary of Chemistry Changes from Baseline (Group B-Natural Lesions)	Treatment column will not be displayed.	SAC
2.6.	Safety	LB3	Summary of Emergent Chemistry Results Relative to Normal Range (Group B-Natural Lesions)	Treatment columns will be replaced by one 'Part B' column	SAC
Laboratory: Hematology					
2.7.	Safety	LB1	Summary of Hematology Changes from Baseline (Group B-Natural Lesions)	Includes baseline values. Treatment column will not be displayed.	SAC
2.8.	Safety	LB3	Summary of Emergent Hematology Results Relative to Normal Range (Group B-Natural Lesions)	As notes for Chemistry T2.12.	SAC
Laboratory: Urinalysis					
2.9.	Safety	LB1	Summary of Urine Concentration Changes from Baseline (Group B-Natural Lesions)	Includes Baseline values. Treatment column will not be displayed.	SAC
2.10.	Safety	LB2	Summary of Emergent Urinalysis Dipstick Results (Group B-Natural Lesions)	As above for Chemistry, using dipstick categories.	SAC
Laboratory: Hepatobiliary (Liver)					
2.11.	Safety	LIVER1	Summary of Liver Monitoring/Stopping Event Reporting (Group B-Natural Lesions)	Treatment columns will be replaced by one 'Part B' column	SAC

Safety : Tables					
No.	Population	IDSL / TST ID / Example Shell	Title	Programming Notes	Deliverable [Priority]
2.12.	Safety	LIVER10	Summary of Subjects Meeting Emergent Hepatobiliary Laboratory Abnormality Criteria (Group B-Natural Lesions)	Treatment columns will be replaced by one 'Part B' column	SAC
ECG					
2.13.	Safety	EG1	Summary of ECG Findings (Group B-Natural Lesions)	Treatment columns will be replaced by one 'Part B' column	SAC
2.14.	Safety	CP_EG11	Summary of Maximum Emergent QTc Values by Category (Group B-Natural Lesions)	Treatment columns will be replaced by one 'Part B' column	SAC
2.15.	Safety	EG2	Summary of Change from Baseline in ECG Values by Visit (Group B-Natural Lesions)	Note: IDSL shell in development. Includes Baseline values. Treatment columns will be replaced by one 'Part B' column	SAC
2.16.	Safety	CP_EG12	Summary of Maximum Change from Baseline in QTc Values by Category (Group B-Natural Lesions)	Treatment columns will be replaced by one 'Part B' column	SAC
Vital Signs					
2.17.	Safety	VS1	Summary of Change from Baseline in Vital Signs by Visit (Group B-Natural Lesions)	Treatment column will not be displayed.	SAC
2.18.	Safety	VS3	Summary of Emergent Vital Signs Results Relative to Normal Range (Group B-Natural Lesions)	Treatment columns will be replaced by one 'Part B' column	SAC
Local Tolerability					
2.19.	Safety	SAFE_T1	Summary (Absolute and Change from Baseline) of Mean irritation score assessment – (Group B-Natural Lesions)		SAC
2.20.	Safety	SAFE_T2	Assessment of Maximum Dermal Reactions and Response (Group B-Natural Lesions)		SAC

